8.8. Full RCT design adaptation

The pilot data will help estimate the effect size and variability of the primary and secondary outcomes, both of which will be crucial for refining the required sample size and ensuring the power of the full RCT.

The pilot study will provide initial estimates of the intervention's effect size, which is the expected difference between the experimental and control groups for each primary and secondary outcome (e.g., smoking cessation rates, alcohol consumption, physical activity). By calculating the mean differences or standardised effect sizes (e.g., Cohen's d) based on the pilot data, we will be able to refine our hypothesis for the full RCT, ensuring that the study is powered to detect a meaningful difference. These estimates will be particularly useful if the observed effect size in the pilot study differs from initial assumptions, allowing for adjustments to the sample size calculation for the full trial.

The pilot study will also provide crucial information on the variability of the outcomes within each group, which directly influences the precision of effect size estimates and, consequently, the power calculation. By assessing the variance or standard deviation of outcomes, we can refine the estimate of variability that will be used in the power analysis for the full RCT. A better understanding of variability, including potential baseline differences or within-group heterogeneity, will allow for more accurate planning of the full RCT's sample size to achieve the desired statistical power.

With the pilot data informing both effect size and variability, the sample size calculation for the full RCT can be adjusted accordingly. For example, if the pilot data indicates a smaller effect size than initially anticipated, the sample size may need to be increased to maintain adequate power. Conversely, if the pilot data reveals lower-than-expected variability, a smaller sample size may suffice.

9. Regulatory, Ethical, and Study Oversight Considerations

The framing governance for the iBeChange studies, including this pilot study, is founded in the GDPR Data Protection by Design and Default recommendations. This has provided the project a basis to assess data protection requirements from the outset, incorporating a Data Protection Impact Assessment (DPIA) and a Data Management Plan (DMP) that has helped to define the data flows and management for the Project. These have helped to guide the development of a Joint Controller Agreement between partners that will govern the capture and sharing of data within the consortium to achieve the goals of the study.

These processes have also informed the application to local research ethics committees and/or independent review boards for local approvals prior to the studies' commencement. These boards will also review the participant information brochures and consent forms provided to potential participants as part of recruitment.

The DPIA and DMP will be continuously updated and are currently being adapted to meet the requirements of the AI Act and expectations around trustworthy AI use and deployment. iBeChange as a Consortium will be making standard risk management around AI, focusing on transparency, data governance, security and privacy, system safety, traceability and explainability for the AI components that are being developed to make recommendations across the platform as the work progresses.

Assessments will be iterative, and activities will be adapted in accordance with the identification of any risks that may present themselves through the ongoing data governance work. These will be keyed towards supporting the validation of tooling approaches, data quality readiness assessments and documentation and record keeping for the platform development and operation.

10. Annex

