8.2. Sample size determination

The sample size for the pilot study was determined as 10% of the total sample for the full RCT, which covers its feasibility nature. For the full RCT, assuming a 60% refusal rate, a significance level of 0.05, and a 5% difference between groups, a sample size of 900 participants per group would result in a power of 80%. Therefore, the estimated sample size for the pilot was 180 participants (90 per group).

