Bayesian methods allow for the incorporation of existing knowledge about the probability of different model parameters (in the form of prior distributions) with observed data to generate updated knowledge about the parameters (in the form of posterior distributions). Statistical inferences are then made based on these updated distributions. We will use weakly informative priors, defined a priori based on clinical assumptions and literature, to derive posterior distributions. Sensitivity analyses will assess the robustness of results to different prior assumptions. Bayesian multilevel modelling is particularly well-fit to handle multiple comparisons. Under this framework, adjustment for multiple tests becomes unnecessary, allowing us to explore hypotheses at a granular level while decreasing the risk of reaching spurious conclusions. Furthermore, Bayesian analyses allow for direct probability statements about parameters (population-level results), providing precise parameter estimates without the need for large samples and allowing the determination of zero effects. Finally, Bayesian models provide more intuitively interpretable uncertainty estimates around parameter values than those offered by their frequentist counterparts.

We will implement the Bayesian estimates using the R statistical language⁴² with the rstanarm package,⁴³ which calls the stan package.⁴⁴ Our modelling strategy will use Markov Chain Monte Carlo (MCMC), repeated four times, i.e., four chains, with 1,000 warm-up iterations followed by 3,000 posterior sampling iterations per chain.

We will interpret model results as a point estimate representing the magnitude of each treatment effect (i.e., regression coefficient) and an interval estimate for the precision of that estimate. The median of the posterior distribution for each treatment effect constitutes the point estimate. We will

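### Section 8.8 lets the pilot's observed effect re-size the RCT, but 90 per group measures that effect too imprecisely for the purpose

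*Protocol*

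**What the plan says.** Protocol section 8.2 plans the RCT "assuming a 60% refusal rate, a significance level of 0.05, and a 5% difference between groups", and states that "a sample size of 900 participants per group would result in a power of 80" per cent. The pilot is set at 10% of that: "the estimated sample size for the pilot was 180 participants (90 per group"). No precision target for the pilot is given.

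Section 8.8 then says what the pilot will feed back. It will estimate the effect for each primary and secondary outcome, as a mean difference or Cohen's d, and this will refine the RCT hypothesis. "These estimates will be particularly useful if the observed effect size in the pilot study differs from initial assumptions", because the RCT sample size calculation can then be adjusted. The worked example for effect size is an increase: "if the pilot data indicates a smaller effect size than initially anticipated, the sample size may need to be increased to maintain adequate power". A decrease is spelled out only for lower-than-expected variability. The section says the RCT should be powered for a meaningful difference, but it gives no value for one. It sets no lower bound on n and does not ask for a confidence limit or shrinkage on the pilot estimate.

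Section 8.1 puts the pilot's statistical focus on feasibility rather than on formal testing of efficacy.

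**The concern.** Two different quantities enter a sample size calculation. The target difference should come from what is worth detecting. The nuisance parameters (SD, control-group rate, attrition) should come from data. Section 8.8 takes both from the pilot. If the pilot effect is mostly noise, chance in 180 people decides the size of a trial planned at 1,800: a favourable pilot argues for a trial that is too small, an unfavourable one for a trial that is larger than needed.

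Section 8.5 may reassure a reader on this point, since it describes Bayesian analysis as "providing precise parameter estimates without the need for large samples". With the weakly informative priors planned there, precision still comes mainly from the 90 per group. The question is therefore how wide the pilot's interval is relative to the planning difference, and what that does to a re-sized RCT.

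**Working it through.** **Inputs.** From section 8.2: 900 per group, 80% power, significance level 0.05, "a 5% difference between groups" (read as 5 percentage points), pilot 90 per group. Assumed, because the protocol does not state them: a two-sided test, no pilot dropout, and a control rate of 15% as the working case, with 5% to 47.5% as the range.

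**1. The plan's own figure.** The stated inputs alone do not give 900, since outcome, base rate, sidedness and the use of the refusal rate are not stated. With 15% vs 20%, two-sided 0.05 and no refusal inflation:
n = [1.96·√(2·0.175·0.825) + 0.842·√(0.15·0.85 + 0.20·0.80)]² / 0.05² ≈ 906 per group; power at 900 is 79.8%.
So 15% vs 20% is one scenario consistent with section 8.2. On the standardised scale, 900 per group has 80% power for d = √(2·(1.96 + 0.842)²/900) = √(15.70/900) = 0.132.

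**2. Precision of the pilot effect.**
- Standardised difference: SE = √(2/90) = 0.149; 95% half-width 1.96 × 0.149 = ±0.29.
- 15% vs 20%: SE = √((0.1275 + 0.1600)/90) = 0.0565; half-width ±11.1 points, so about −6 to +16 around a true 5.
- 5% vs 10%: SE 0.0391, ±7.7 points. 47.5% vs 52.5%: SE 0.0744, ±14.6 points.

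The half-width exceeds the 5-point target at every base rate in the range. At 15% vs 20%, the normal approximation gives a probability of 0.188 that the pilot shows no benefit (5/5.65 = 0.885 SE below the truth). By symmetry it gives 0.188 that the pilot shows at least 10 points.

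**3. Re-sizing in both directions on the observed effect (true d = 0.132).** Put the observed d into n = 15.70/d².
- Positive pilots are 81% of the total. Among them, the simulated quartiles of n are 241 and 1,902 per group (normal quantiles give 240 and 1,907), against about 900 needed.
- True power is below 50% when n < 2·(1.96/0.132)² = 441, that is, when observed d > 0.132 × 2.802/1.96 = 0.189. With SE 0.149 this has probability P(Z > 0.0567/0.149 = 0.38) = 35% of all pilots.
- With a pilot of 900 per group, SE = 0.047 and the same event has probability P(Z > 1.20) = 11%.

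A simulation on proportions at 15% vs 20% agrees: quartiles of 234 and 1,689 among positive pilots, and 36% of all pilots below 50% power.

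**4. Re-sizing upwards only from 900.** If the true effect is as planned (14.85% vs 19.85%, for which 900 per group gives 80%), no re-sized RCT is underpowered. At a 15% control rate with a true effect of 3 or 4 points, 2,402 or 1,384 per group are needed, and about 51% of all pilots still leave the RCT below 80% power.

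**5. Variability, for contrast.** A pooled SD on 178 degrees of freedom has 95% limits of about −9% to +12%. The variability half of section 8.8 is therefore sound.

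**The case against.** The strongest reply is that section 8.8 fixes no plug-in rule. Its verbs are permissive, its only effect-size example is an increase, and the decrease it names is for lower variability. Read with 900 as a floor, the shortfall vanishes when the true effect is as planned. Nothing in the pilot's own conduct depends on the section, and RCT protocols are left to later work.

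Much of this stands, and it makes the size of the shortfall conditional. It does not remove the point. The sentence about adjustments covers any difference from the initial assumption, no floor is written, and no other value is given for the target. Even with a floor, the problem remains in the case that the example sentence addresses, a true effect smaller than planned.

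A reader might infer that the small pilot is why half of re-sizings fall short. It is not. Any roughly unbiased estimate lies above the truth half the time, so 50% of all pilots give power below 80% whether the pilot has 90, 900 or 5,000 per group. Moreover, the 50% is a share of all pilots; among those that give a size at all it is about 62% (0.50/0.81). What 90 per group changes is the depth of the shortfall: power below 50% in 35% of pilots, against 11% at 900.

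**Conclusion.** The point holds as a recommendation on RCT planning. Section 8.8 names the pilot's observed effect as a sizing input without safeguards, and 90 per group gives an interval of about ±0.29 SD, or ±8 to ±15 points over base rates of 5% to 47.5%, around a 5-point target. The interval widths rest only on the group size and the assumed base rate. The 241 to 1,902 range and the 35% rest on re-sizing in both directions with a true d of 0.132.

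Four further readings are tempting, but the documents do not support them.
- That 900 per group reproduces only at a control rate near 15%: 80% vs 85%, a one-sided test near 22% vs 27%, or 360 analysed per group (900 × 0.4) near 3.5% vs 8.5% also fit.
- That the refusal rate plays no part in 900: section 8.2 does not say how it enters.
- That early stopping under section 8.6 inflates the pilot estimate: this was not simulated. Section 8.1 aims to finish recruitment within three months, so enrolment may be almost complete before the first look, which needs 25% of the sample to have finished 12 weeks.
- That an unlucky pilot cancels the RCT: the feasibility thresholds in section 8.1 concern consent, missing data, usability, timing and wearable use, not the observed effect.

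**What to change.** In section 8.8:
- Hold the RCT's target difference at a clinically justified value, either the 5 points of section 8.2 or a named minimum important difference for each outcome used for sizing.
- Limit what the pilot may update to SDs, control-group rates, baseline-to-follow-up correlation, attrition and consent.
- Report the pilot's effect estimates with intervals, and state that they are not a sizing input.

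The change is to wording only and leaves the pilot's size, conduct and analysis as they are. It is best made before any pilot effects are seen. The price is that the RCT can no longer be made smaller because the pilot looked favourable; it could still shrink if variability proved lower than expected, as section 8.8 already allows.

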10.1. Clinical Recommendations for Cancer Prevention for Control participants

Please include the text of the 2nd level.

This is an English version translated from the postal letter sent to participants from the Cancer Screening Program at ICO. It will be adapted to Italian and delivered to IEO participants, and adapted to Romanian and delivered to UMFCD participants.

Dear sir/madam,

We thank you for your participation in the cancer screening test.

Until your next screening, please consider these recommendations from the European Code Against Cancer:

- Do not smoke
- Keep a healthy weight
- Do daily physical activity
- Follow a healthy diet
- Avoid alcohol consumption
- Protect your skin from sunlight
- Get vaccinated against some infections
- Regularly undergo cancer screening tests

Prevention is also in your hands!

Adopting these practices contributes to a full and healthy life.

Thank you for participating in iBeChange!

iBeChange team
ICO/IEO/UMFCD team

10.2. List of Standardized Criteria for Level 3 intervention escalation

If any of the items listed below are suspected in a participant during the professional SSI, they will be referred to external professional assistance but keep the iBeChange support in parallel:

- Depressed mood most of the day, for at least 2 consecutive weeks, represents a difference from previous functioning.
- Important decrease in interest or pleasure in almost all activities most of the day, for at least 2 consecutive weeks, representing a difference from previous functioning.

NOTE: Ensure these two risk factors are not due to a recent bereavement process.

- Excessive worry about various events presents more than half the time for approximately 6 months.
- Other anxiety symptoms include: feeling restless, tense, panic, experiencing periods of
 increased heart rate, hyperventilation, sweating, trembling, or having trouble
 concentrating. These symptoms significantly interfere with the person's daily
 functionality.
- Indicators of Post-Traumatic Stress Disorder: 1) memories, nightmares, flashbacks; 2) persistent avoidance; 3) intense physiological reactions of hyper-arousal or other behaviours as if the traumatic event were occurring. These symptoms cause significant emotional distress and last more than 1 month.
- Risk behaviours or self-harm (including substance abuse and eating disorders).
- Recurrent thoughts of death or suicide.
- Significant cognitive impairment.
- Active psychotic symptomatology: disorientation (in time, place, or person), severely disorganised thinking and/or behaviour, hallucinations, and delusional ideas.
- Being a victim of psychological or physical abuse.
- Any other psychological symptom that generates significant functional impairment in any area of their life.

11. Conclusions

This deliverable presents the finalised protocol for the iBeChange pilot study, a foundational step within Work Package 5 aimed at evaluating the feasibility and usability of a digital behavioural change platform for cancer prevention. The protocol outlines the key procedures and methodological framework to be implemented across participating clinical sites, including recruitment, intervention delivery, assessment timelines, and data management. Importantly, this pilot study also integrates outcomes from Work Package 2 — Design of the integrated platform using Behaviour Change Techniques and a User-Centred Design approach. Specifically, the selection of representative outcomes related to lifestyle and psychosocial risk and protective factors, developed through Tasks 2.1 and 2.2, has directly informed the data collection strategy for T2.5 (Patient-Reported Outcome Measures, lifestyle, and psychosocial variables) and the development of the behavioural change and psychological support tool under T2.7.

This pilot also included the wearable sub-study, which is integrated into the same randomisation structure as the main study (as a second randomisation). This sub-study explores the potential of wearable technology to passively collect lifestyle and psychosocial data. While briefly described within this protocol for ethical submission purposes, further detail is provided in a separate deliverable (D5.2).

The pilot study will provide essential insights into the logistical and methodological aspects of deploying the iBeChange intervention, allowing for refinements before launching the full-scale randomised controlled trial (iBC/CT). Findings from the pilot will also help validate the tools and technologies used (such as REDCap and the Point of Care platform), and assess participant adherence, recruitment feasibility, and the suitability of outcome measures.

Future work includes the formal submission of this protocol to ethics committees across participating centres, its registration in relevant public repositories (WHO International Clinical Trials Registry Platform; ICTRP), and its publication in open-access, peer-reviewed scientific journals to promote transparency and facilitate knowledge sharing. Insights gathered from the pilot will inform adjustments to the intervention and study design ahead of the larger randomized controlled trial planned within WP5.

Other relevant future work will involve:

